5. Chronic kidney disease caused by glomerulonephritis, tubulo-interstitial nephritis), Obstructive uropathy or autosomal dominant polycystic kidney, and Kidney disease from other causes

6. Diabetes with HbA1c > 8 or uncontrollable hypertension

7. Active malignancy of cancer in other organs in the last 3 years

8. History of receiving non-steroidal anti-inflammatory drugs (NSAIDs) or other nephrotoxic drugs within the past 1 month (except tenofovir)

(For patients receiving NSAIDs after participating in this study, patients were advised to stop taking NSAIDs but not exclude from the study)

9. Receive immunosuppressive drug

10. Pregnancy

Withdrawal or termination criteria

1. GFR reduction was less than 15 ml / min

2. Receive renal replacement therapy

3. Receive a liver or kidney organ transplant.

4. Request to withdraw from their participation in the study.

5. Develop HCC.

Sample size calculation

From a literature review, It was found that the average value of the eGFR level of the TDF group was -5.34 ± 7.69 (n = 45) (95% CI: -7.65 - -3.02) and the mean value of the eGFR in TAF group was $+2.89. \pm 4.26$ (n = 36) (95% CI: 1.45 - 4.33) But from the Siriraj hospital observations during 2018, the mean The eGFR change value level is +5.92 after TDF dose adjustment. Therefore, from the above data, when determining the significance level = 0.05 (type I error = 5%, 2-sided) and power of the test = 80% (type II error = 20%), 33 samples would be needed in each group

$$n = \frac{(Z_{\alpha/2} + Z_{\beta})^2 (\sigma^2)}{(\mu_1 - \mu_2)^2}$$

$n =$ samples would be needed in each group

$\alpha =$ type I error = 0.05 ($Z_{\alpha/2} = 1.96$)

$$\beta = \text{type II error} = 0.20 \quad (Z_{\beta} = 0.84)$$

σ = standard deviation

$\mu_1 - \mu_2$ = The difference of mean values between groups

$$n = \frac{(1.96 + 0.84)^2 (4.26^2)}{(5.92 - 2.89)^2} = 33$$

From the calculations, it was found that at least 33 samples were used per group. After add dropout rate 15%, So 40 samples are to be used per group, a total of 80 people in this study.

Statistical analysis

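### The sample-size equation equals 15.5, not 33, and uses only the smaller (TAF) SD; with both SDs the protocol quotes, 33 per group gives about 49% power, not 80%

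*Combined protocol and SAP*

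**What the plan says.** The section headed Sample size calculation in the combined protocol and SAP starts from literature values for change in eGFR. For TDF, "average value of the eGFR level of the TDF group was -5.34 ± 7.69 (n = 45"; for TAF, the mean is +2.89 with SD 4.26 (n = 36). It then replaces the TDF mean with a local observation from 2018: "The eGFR change value level is +5.92 after TDF dose adjustment". No SD is given with that figure.

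The error rates are "significance level = 0.05 (type I error = 5%, 2-sided" and 80% power. The conclusion is "power of the test = 80% (type II error = 20%), 33 samples would be needed in each group". The printed equation multiplies (1.96 + 0.84)² by 4.26², divides by (5.92 − 2.89)² and sets the result equal to 33. With 15% dropout this becomes 40 per group, 80 in total.

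Section 8.8.2 lists eGFR first among the outcomes to be compared over 48 weeks, by repeated measures ANOVA or Friedman's test.

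**The concern.** There are two separate faults.

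- **The equation does not give its own answer.** It has one variance term, although the section defines n as a per-group number and the denominator as a difference between groups. A comparison of two independent means needs the sum of the two arm variances.
- **Only the smaller of the two quoted SDs is used.** The local figure replaces the TDF mean, and the TDF SD is dropped along with it. The TAF SD then stands in for both arms, without a stated reason.

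The claimed 80% power is at stake. If the dose-adjusted TDF arm varies as the quoted TDF group did, a true difference of 3.03 ml/min would be missed about half the time. The plan sets no equivalence or non-inferiority margin, so a null result from 80 patients could be misread as showing that the two strategies are the same for renal function.

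**Working it through.** **Inputs, all from the Sample size calculation section.** Two-sided alpha 0.05 (1.96); power 80% (0.84); means +5.92 (TDF, local) and +2.89 (TAF), difference 3.03; SDs 7.69 (TDF, n = 45) and 4.26 (TAF, n = 36); 40 per group planned, of whom 40 × 0.85 = 34 remain after 15% dropout.

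**Step 1. Are the ± values SDs?** The t-based 95% intervals are:

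- TDF: −5.34 ± 2.015 × 7.69/√45 = −7.65 to −3.03 (printed −7.65 to −3.02)
- TAF: 2.89 ± 2.030 × 4.26/√36 = 1.45 to 4.33 (printed 1.45 to 4.33)

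They are SDs, not standard errors.

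**Step 2. The equation as printed.** 7.84 × 4.26² / 3.03² = 7.84 × 18.15 / 9.18 = **15.5**, so 16 per group.

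**Step 3. Where 33 could come from.**

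- Two-sample formula with SD 4.26 in both arms: 2 × 15.50 = 31.0. The t-based version gives **33** (power 79.98% at 32 and 81.2% at 33).
- Printed formula with the average of the two quoted variances: 7.84 × [(59.14 + 18.15)/2] / 9.18 = 32.998. This uses both SDs but still omits the factor of 2, and it does not match the 4.26² actually printed.

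The document does not say which route was taken. The first is the more natural reading.

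**Step 4. Two-sample formula with both quoted SDs.** n = 7.84 × (7.69² + 4.26²) / 3.03² = 7.84 × 77.28 / 9.18 = **66.0** per group, or 68 with the t distribution.

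**Step 5. Power at the planned sizes** (two-sided 5% t-test on change in eGFR, noncentral t, Satterthwaite degrees of freedom). At 33 per group with both quoted SDs, the standard error of the difference is √(77.28/33) = 1.53 and the noncentrality is 3.03/1.53 = 1.98.

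| Per group | Power for 3.03, SDs 7.69 and 4.26 | Difference detectable with 80% power, same SDs | Power for 3.03, SD 4.26 in both arms |
|---|---|---|---|
| 33 | 49% | 4.4 ml/min | 81% |
| 34 | 50% | 4.3 ml/min | 82% |
| 40 | 57% | 4.0 ml/min | 88% |

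**Step 6. Sensitivity to the unknown TDF SD, at 34 per group, TAF SD 4.26.**

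| TDF SD | 4.26 | 5 | 6 | 7 | 7.69 |
|---|---|---|---|---|---|
| Power | 82% | 75% | 66% | 56% | 50% |

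Power falls below 80% once the TDF SD exceeds about 4.5.

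**Step 7. Dropout.** 33/0.85 = 38.8, so 39 against 40 planned. The dropout allowance is adequate for the target of 33; the problem lies in the target.

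**The case against.** The strongest reply is that 33 is a correct target under one clear assumption, an SD of 4.26 in both arms. On that view the missing factor of 2 is a display error that changes neither the sample size nor the power. This stands for the number 33. It leaves the equation wrong and the equal-SD assumption unstated, beside a quoted SD that contradicts it.

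The second reply is that 7.69 belongs to a literature TDF group whose mean change was −5.34, whereas the trial arm is dose-adjusted TDF with an expected change of +5.92. Nothing shows that 7.69 carries over. This also stands, and it makes the 49% conditional. But nothing shows that 4.26 carries over either, since it comes from patients on a different drug. At 34 per group, a TDF SD only slightly above 4.26 already takes power below 80%.

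Third, the planned eGFR analysis is repeated measures ANOVA or Friedman's test, and its power could differ from that of a t-test on change. That is true. However, the documents give no within-patient correlation from which to compute it, and the protocol's own calculation compares two means.

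Finally, the plan makes no equivalence claim, so the harm lies in how a null result might be read. That is correct, and it is why a sentence on interpretation is enough to address it.

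**Conclusion.** The concern holds. The printed equation equals 15.5, not 33; this needs no assumption. The 80% power claim requires the TDF arm to have an SD close to that of the TAF arm, which the protocol neither states nor supports. For 3.03 ml/min at 33 per group, power is 81% if the dose-adjusted TDF SD is 4.26 and 49% if it is the quoted 7.69. In the second case 80% power needs 68 per group before dropout, about twice the plan.

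These figures rest on a two-sided 5% comparison of mean change between two independent arms. The arithmetic is certain; the SD of the dose-adjusted arm is not known from the documents. The section has to be corrected because the equation is wrong as written and the stated power is not supported by the variability figures quoted beside it.

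**What to change.** In the Sample size calculation section:

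1. Replace the formula with n = (Zα/2 + Zβ)²(σ₁² + σ₂²)/(μ₁ − μ₂)² and enter an SD for each arm. If the 2018 hospital data behind +5.92 yield an SD, report it and use it for the TDF arm. Otherwise use 7.69 and say that it comes from the literature group.
2. Keep 80 patients and restate what they deliver with 34 evaluable per group: about 50% power for 3.03 ml/min with SDs 7.69 and 4.26 (82% only if both SDs are 4.26), or 80% power for about 4.3 ml/min with SDs 7.69 and 4.26.
3. Add to the statistical analysis section that a non-significant eGFR comparison will be interpreted from the 95% confidence interval for the difference and not as evidence of equivalence.

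The cost is protocol wording and a less favourable power statement. No extra patients are needed. The change does not restore 80% power for 3.03 ml/min; it makes the stated power match the figures.

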8.8.1 Descriptive statistics

Demographic data such as qualitative variables such as gender, presented in frequency and percentage.

The quantitative variables, such as age, that are continuous data, presented with the mean and standard deviation (SD) if the data has a normal distribution. However, if the data doesn't have a normal distribution, presented with the median and minimum-maximum values.

8.8.2 Inferential statistics

- Comparison of changes in eGFR, serum phosphate, urine protein creatinine ratio, urine phosphate, urine β 2-microglobulin, AST, ALT, HBV DNA between the treatment with TAF and adjusted dose TDF for 48 weeks by using the Repeated measures ANOVA or Friedman's test.

- Comparison of the change in urine NGAL between the treatment with TAF and adjusted dose TDF for 48 weeks by using Independent T test or Mann whitney test

Data recording and analysis using SPSS programme

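### Section 8.8.2 gives urine protein/creatinine ratio and β2-microglobulin no usable between-arm test except untransformed ANOVA, which can cost substantial power if these markers are strongly right-skewed

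*Combined protocol and SAP*

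**What the plan says.** The first line of section 8.8.2 reads "Comparison of changes in eGFR, serum phosphate, urine protein creatinine ratio, urine phosphate". The list goes on to urine β2-microglobulin, AST, ALT and HBV DNA. All of these are to be compared between TAF and adjusted-dose TDF over 48 weeks "by using the Repeated measures ANOVA or Friedman's test". No log transformation, ratio to baseline or other scale is named, and there is no rule for choosing between the two tests.

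Urine NGAL has its own line and is compared "by using Independent T test or Mann whitney test", so that marker does have a rank test between two independent groups.

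Section 8.8.1 allows for non-normal quantitative data, which are "presented with the median and minimum-maximum values". That rule concerns description only.

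The visit table schedules urine protein/creatinine ratio at five visits (weeks 0, 12, 24, 36, 48) and urine β2-microglobulin at four (weeks 0, 12, 24, 48). The only power statement, under Sample size calculation, is for eGFR change. No SD, distribution or target effect is given for any urine marker.

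**The concern.** Urine protein/creatinine ratio and β2-microglobulin are positive quantities. If they differ between patients by multiples, a treatment that lowers them proportionally produces large absolute changes in the few patients who start high and small ones in everyone else. The raw difference in mean change, and its standard error, are then driven by those few patients.

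The alternative named in 8.8.2 does not help. Friedman's test asks whether values differ across visits within patients, and it has no arm factor. If the data look non-normal and the analyst moves to Friedman's test, the TAF versus TDF comparison is lost for that marker. If the analyst stays with ANOVA, the comparison is on the raw scale unless something is added that the plan does not mention.

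At stake is the ability to detect a difference between arms in these renal markers, and to summarise it in a way that a handful of patients does not dominate.

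**Working it through.** **The plan's own figure.** The documents give none for urine markers; the only one is for eGFR. The formula as printed gives (1.96 + 0.84)² × 4.26² / (5.92 − 2.89)² = 7.84 × 18.1476 / 9.1809 = 15.5. With the usual two-sample factor of 2 this is 31.0, or 32 with a t-based calculation, against 33 stated. So 33 reproduces closely, but only with a factor that the printed formula omits. Allowing for dropout, 33 / 0.85 = 38.8, i.e. 39, against 40 stated. This matters here only because it fixes the number of patients: 40 × 0.85 = 34 completers per arm.

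**Inputs for the urine markers**
- From the documents: 34 per arm (above), two-sided 5% level, five visits (protein/creatinine ratio) or four (β2-microglobulin).
- Assumed: lognormal marker with SD of log *s* from 0.5 to 1.3; between-visit correlation *r* on the log scale of 0.6 or 0.8; one arm halving the marker at every post-baseline visit.

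**Closed-form check for one change from baseline (normal approximation).**

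Log scale: z = ln 2 / [s·√(2(1 − r))·√(2/34)].

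Raw scale, in units of the baseline mean: the difference in mean change is 0.5. The variance of change is 2(e^{s²} − e^{rs²}) in the unchanged arm and 1.25(e^{s²} − 1) − (e^{rs²} − 1) in the halving arm. Then z = 0.5 / √[(sum of the two variances)/34]. Power ≈ Φ(z − 1.96) on either scale.

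For s = 1.0, r = 0.6:
- Log: z = 0.693 / (0.894 × 0.2425) = 3.20, power Φ(1.24) = 89%.
- Raw: variances 1.792 and 1.326; z = 0.5 / √(3.118/34) = 1.65, power Φ(−0.31) = 38%.

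The same formulas give raw versus log power of 66% versus 98% at s = 0.8, r = 0.6, and 16% versus 69% at s = 1.3, r = 0.6.

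**Simulation of the test itself.** This used the group-by-visit F test with Greenhouse-Geisser correction on raw and on log values. Ranges run over r = 0.6 to 0.8.

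| Assumed SD of log | Raw power | Log power |
|---|---|---|
| 0.5 | about 100% | about 100% |
| 0.8 | 68-90% | 99-100% |
| 1.0 | 40-65% | 90% to >99% |
| 1.3 | 15-29% | 70-96% |

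The closed form agrees with these. With no treatment effect the raw test rejects about 1% to 6% of the time and the log test about 4% to 6%.

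**A smaller effect.** Here the effect was set so that a t test on log change has 80% power (33 per arm, r = 0.7, four visits; no sphericity correction). Log versus raw ANOVA power is 83% versus 77% at SD of log 0.3, 83% versus 68% at 0.5, 82% versus 50% at 0.8, 83% versus 40% at 1.0 and 83% versus 21% at 1.5. Mann-Whitney on raw change gives 73%, 69%, 62%, 58% and 55% in the same settings. In skewed data a correct rank test therefore recovers part of the loss, but less than a change of scale does.

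**The case against.** - **A rank test is offered.** The plan does foresee non-normal data and names a non-parametric option in the same sentence. That is so, but the option named cannot compare two independent arms. The plan is silent on scale and does not mandate raw values; raw is simply what results when nothing else is stated.
- **The loss depends on an assumption.** A reader might infer that most of the power is lost, or that a halving would probably be missed. The documents do not support this, because they give no spread for any of these markers. Under a halving there is essentially no loss at an SD of log of 0.5, and at 0.8 raw power is still 68-90%. More than half of the power goes only from an SD of log of about 1.0 upward, and at 1.0 with correlation 0.8 the raw test would still more likely than not detect a halving. The exclusions for other kidney disease, poorly controlled diabetes and uncontrollable hypertension may also narrow the spread. This stands.
- **The simulation favours the log scale.** Lognormal data with a proportional effect are the case that log analysis fits by construction. This stands as a limit on the figures.
- **Urine phosphate may differ.** Nothing in the documents shows that it is as skewed as the other two. This stands; including it is an assumption.
- **Limited consequence.** A reader might also infer false-positive findings or an inadequate sample size. Neither follows: the raw test does not materially exceed its nominal error rate, and the sample size rests on eGFR.

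**Conclusion.** The point holds as a should-fix gap in the analysis plan. What the text establishes without any assumption is that, for urine protein/creatinine ratio, β2-microglobulin and urine phosphate, section 8.8.2 names one test that can compare the arms, with no transformation, and one that cannot.

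The size of the consequence is conditional. For a halving it runs from nothing at an SD of log of 0.5, through roughly 10 to 31 points at 0.8 (100 − 90 and 99 − 68), to about 50 points or more at 1.0 with correlation 0.6 (90 − 40), and larger losses at 1.3. For the smaller calibrated effect, the loss is already 15 points at 0.5 (83 − 68). These figures rest on assumed spread, correlation, effect size and lognormal shape. The log figures are for the same group-by-visit test on log values, not for the baseline-adjusted model proposed below. The case for acting does not depend on where in the range the markers fall: the log scale did at least as well as raw in every skewed setting examined.

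**What to change.** In section 8.8.2:
1. State that urine protein/creatinine ratio and urine β2-microglobulin (and urine phosphate, on the assumption that it is similarly skewed) are analysed on the log scale in the between-arm repeated-measures model, adjusted for log baseline.
2. Report, for each, the TAF/TDF ratio of geometric mean fold-change from baseline to week 48 with 95% CI.
3. For these markers, replace Friedman's test with a between-arm rank test of change (Mann-Whitney, as already planned for NGAL), labelled as a sensitivity analysis. This also removes a choice between two tests that could otherwise be made after seeing the data.
4. State how any values below the assay limit are substituted before taking logs.

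The cost is a few sentences in the plan and no new data or visits. Effects will be reported as ratios instead of absolute differences, and the substitution rule has to be fixed in advance. The sample size of 40 per group does not change.

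### Section 8.8.2 tests eGFR change by repeated measures ANOVA without naming the tested effect or a safeguard against non-sphericity or unequal arm variances, so the type I error can depart from 5%

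*Combined protocol and SAP*

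**What the plan says.** The inferential section (8.8.2) covers eGFR and seven other measures in one sentence: changes are compared "between the treatment with TAF and adjusted dose TDF for 48 weeks by using the Repeated measures ANOVA", or else by Friedman's test. The only other detail on method is "Data recording and analysis using SPSS programme". The section does not say:

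- whether the group-by-visit interaction or the between-arm main effect answers the question;
- whether week 0 is one of the repeated values or is subtracted first;
- which p-value is read if sphericity fails;
- what is done if the arms have different variances.

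The visit table schedules creatinine, and so eGFR, at weeks 0, 12, 24, 36 and 48. The sample size section plans on eGFR change at "significance level = 0.05 (type I error = 5%, 2-sided"). It cites a literature result in which "the TDF group was -5.34 ± 7.69 (n = 45") and a TAF result of +2.89 ± 4.26 (n = 36, "95% CI: 1.45 - 4.33"). It then turns to local data, "The eGFR change value level is +5.92 after TDF dose adjustment", for which no SD is given. The calculation uses 4.26 for both arms.

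**The concern.** Repeated measures ANOVA makes two assumptions that matter here. The uncorrected within-patient F test needs sphericity: the difference between any two visits must have the same variance. The test also pools one covariance matrix over both arms.

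Sphericity is doubtful for eGFR over 48 weeks. If patients follow different slopes, the week 0 to 48 difference varies more than the week 36 to 48 difference. A common covariance is also open to question, because the protocol's own literature SDs differ 1.8-fold. Friedman's test is no fallback, since it ranks visits within patients and does not compare arms.

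At stake is the error rate for the outcome that sized the trial. With no rule fixed in advance, several p-values with different true error rates are available from the same output.

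**Working it through.** **1. The plan's own figures.** The formula as printed gives 2.80² × 4.26² / 3.03² = 15.5. With the usual factor 2 for two groups it gives 31.0, and the t-based solution is 32.02, which rounds up to 33. So 33 agrees with the standard two-sample calculation, although the printed formula lacks the factor. With 40 per arm and 15% dropout, 40 × 0.85 = 34 completers per arm.

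Both literature SDs reproduce their printed intervals: −7.65 to −3.03 for n = 45, and 1.45 to 4.33 for n = 36. The variance ratio is 59.14 / 18.15 = 3.26 (two-sided F test on 44 and 35 df, p = 0.0005).

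**2. Assumed model.** The documents give no within-patient correlation. Assume a patient-specific linear drift with variance v over 48 weeks, plus independent noise of SD σ = 1.5 to 3.0 ml/min at each visit. Scale it so that the SD of week-48 change is s: v = s² − 2σ².

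**3. How far from spherical.** Take σ = 2.0 and the average of the two variances, (59.14 + 18.15)/2 = 38.64.

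- v = 38.64 − 8 = 30.64.
- Variance of the week 0 to 48 difference: 38.64. Week 36 to 48: 30.64/16 + 8 = 9.92.
- With time scaled 0 to 1, the squared deviations of the five visit times sum to 0.625. The eigenvalues of the contrast covariance are 0.625 × 30.64 + 4 = 23.15, then 4, 4 and 4.
- ε = (23.15 + 12)² / [4 × (23.15² + 3 × 16)] = 1235.5 / 2335.7 = 0.53.

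The approximate size of the uncorrected five-visit F is 5.7% at ε = 0.9, 7.3% at 0.7 and 9.4% at 0.5.

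**4. Simulated type I error with no arm difference, 34 vs 34, uncorrected group-by-visit F** (10,000 trials per setting; ranges cover repeat runs):

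| Change SDs | σ = 1.5 | 2.0 | 2.5 | 3.0 |
|---|---|---|---|---|
| 7.69 / 4.26 | 9.6–10.2% | 7.8–8.5% | 6.5–7.1% | 5.7–6.5% |
| 6.22 / 6.22 (same average variance) | 10.3% | 8.3% | 6.8% | 5.7% |
| 4.26 / 4.26 | 8.0% | 6.1% | 5.4% | 5.0% |

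The first two rows agree within simulation error, so with equal arms the SD ratio adds essentially nothing. In the last cell v = 18.15 − 18 = 0.15, which is almost spherical, hence 5.0%.

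For SDs of 7.69 and 4.26 in the same setting, Greenhouse-Geisser gives 4.5% to 5.2% and the between-arm main effect 4.6% to 5.3%.

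Other assumed structures, at 33 or 40 per arm, give 5.1% to 5.3% when near-spherical and 5.7% to 8.6% under AR(1), random-walk or stronger random-slope covariance.

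**5. Unequal completers with SDs 7.69 and 4.26.** For week-48 change, compare the true variance of the arm difference with the pooled estimate.

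- 28 (more variable arm) vs 38: true 59.14/28 + 18.15/38 = 2.590. Pooled [(27 × 59.14 + 37 × 18.15)/64] × (1/28 + 1/38) = 35.44 × 0.0620 = 2.198. Ratio 1.178. The cut-off 1.96 acts as 1.96/√1.178 = 1.81, a size of about 7.1%.
- 38 vs 28: true 2.204, pooled 41.84 × 0.0620 = 2.596, ratio 0.849. The effective cut-off is 2.13, a size of about 3.3%.

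Simulation of the five-visit test agrees:

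| Completers (SD 7.69 arm vs SD 4.26 arm) | Uncorrected F | Greenhouse-Geisser |
|---|---|---|
| 28 vs 38 | 7.8–13.4% | 6.5–7.7% |
| 38 vs 28 | 4.6–7.4% | 3.1–3.8% |

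A Welch comparison of week-48 change gives 4.6% to 5.6% throughout.

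**The case against.** The strongest reply is that the plan is brief rather than wrong. It does not commit to the uncorrected interaction test. SPSS offers the corrections, and with the planned 1:1 arms the Greenhouse-Geisser test and the between-arm main effect both hold 5%. The correlation model is assumed, and under a near-spherical one there is hardly any inflation. All of this stands, and it limits the 6% to 10% figure to one choice of test under one family of models. It does not remove the gap, because nothing in 8.8.2 excludes that choice.

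A reader might go further and infer any of the following. The documents do not support them.

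- *That the 1.8-fold SD ratio causes the inflation.* With equal arms it does not, as the equal-SD comparison shows.
- *That this ratio will hold in the trial.* The 7.69 belongs to a literature TDF group that lost 5.34. The protocol set that mean aside in favour of +5.92 and gives no SD for adjusted-dose TDF.
- *That unequal completers always raise the error.* The effect reverses with direction.
- *That the renal withdrawal rules will shrink the TDF arm.* The planning means (+5.92 against +2.89) do not predict this. The listed GFR withdrawal threshold is 15 ml/min, and the change of drug below 30 is not listed as withdrawal.
- *That 28 vs 38 is expected.* It means losing 12 of 40 (30%) in one arm and 2 of 40 (5%) in the other, against a planned 15%. It is a stress case.

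**Conclusion.** The concern holds as a gap in specification with a measurable consequence. If the uncorrected group-by-visit F is read, its type I error is about 6% to 10% with equal arms under the random-slope model with SDs 7.69 and 4.26, and about 5% to 8% with 4.26 in both arms. That inflation comes from non-sphericity and rests on a correlation structure the documents do not give. A Greenhouse-Geisser correction removes it while the arms stay equal.

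The correction is not enough if two further conditions both hold: arm SDs as unequal as in the cited literature, and different numbers of completers. The size is then about 7% or about 3%, depending on which arm is smaller.

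It would be too strong to say that the trial's p-value will be wrong, since the plan does not say which p-value it will use. The change should be made because it is cheap and settles the tested effect as well as the error rate.

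**What to change.** In 8.8.2, name the week-48 arm contrast in eGFR change as the test. Take it from either:

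- a mixed model for repeated measures with unstructured visit covariance (SPSS MIXED, Satterthwaite degrees of freedom), with the covariance allowed to differ by arm; or
- a Welch comparison of week-48 change.

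State which of the two is the inference. If repeated measures ANOVA is kept as supportive, always report the Greenhouse-Geisser-corrected p-value, and do not let Mauchly's test decide whether to correct.

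The cost is SAP wording and a few degrees of freedom for the extra variance parameters. No new data, visits or software are needed.

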[figure not shown]
Randomized trial of
tenofovir disoproxil fumarate dose adjustment VS. switching to tenofovir alafenamide
in tenofovir disoproxil fumarate-experienced chronic hepatitis B patients with renal impairment

SIRB Protocol No. : 657/2562(EC3)

COA no. : SI 798/2019

Document date : 25 Nov 2019

Study protocol

| | Week 0 | Week 12 | Week 24 | Week 36 | Week 48 |
|---|---------------|----------------|----------------|----------------|----------------|
| History taking and physical examination | X | X | X | X | X |
| CBC | X | | | | X |
| Creatinine, BUN, Uric acid, Calcium, Phosphate, Electrolyte | X | X | X | X | X |
| AST/ALT | X | X | X | X | X |
| HBV DNA viral load | | | X | | X |
| urinalysis, urine protein creatinine ratio, urine phosphate | X | X | X | X | X |
| urine β 2-microglobulin | X | X | X | | X |
| urine NGAL | X | X | | | |
| ultrasonography of upper abdomen | | | X | | X |

- Some blood tests may be stored before -20 ° C for later tests.

- Some urine tests may be stored before -30 ° C for later tests.

Monitoring and follow-up guidelines in the event that patients receiving TDF dose adjustment or change to TAF and the kidney function deterioration.

- If the GFR from 40 ml/min or more: Make appointment for examination every 12 weeks

- If the GFR is less than 40 ml/min: Make appointment every month

- If the GFR is less than 30 ml/min: Change to Entecavir (1mg) 1 * 1 po pc

If patient will have to check up earlier than 12 weeks, there will be a travel cost of 300 baht per time.

However, if the patient comes to the same appointment every 12 weeks, there will be no travel cost.

Inclusion criteria

1. Age between 18 - 75 years old

2. Chronic hepatitis B virus infection

3. Reduced renal function and need to adjust the dose of TDF

4. Have an eGFR of ≥ 15 ml / min.

5. HBV DNA viral load levels ≤ 10 U/mL in the last 3 months before participating in the project

6. No HCC by ultrasonography of the upper abdomen or CT 3-phase of liver or MRI liver in the 3 months before participating in the project.

Exclusion criteria

1. HIV infection or hepatitis C or hepatitis D co-infection

2. Decompensated cirrhosis, including variceal bleeding, ascites, hepatic encephalopathy

3. Active hepatocellular carcinoma or during the 3 years after treatment

4. Solid organ transplantation or Bone marrow transplantation

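### Friedman's test, the named alternative to repeated measures ANOVA, does not use the treatment arm, so outcomes analysed with it get no valid TAF versus TDF comparison.

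*Combined protocol and SAP*

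**What the plan says.** Section 8.8.2 (Inferential statistics) opens with "Comparison of changes in eGFR, serum phosphate, urine protein creatinine ratio, urine phosphate" and continues with urine β2-microglobulin, AST, ALT and HBV DNA, eight outcomes in all. It states the aim as a comparison between TAF and "adjusted dose TDF for 48 weeks by using the Repeated measures ANOVA or Friedman" (Friedman's test). The title describes a randomised trial of two strategies, so the arms contain different patients.

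For urine NGAL the same section compares the arms "by using Independent T test or Mann whitney test". That is a valid pair of two-sample tests, but no between-arm rank test is named for the other eight outcomes.

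No rule says when Friedman's test replaces ANOVA. The only normality rule is in section 8.8.1 and concerns the choice of summary statistics: variables that do not "have a normal distribution, presented with the median and minimum-maximum values".

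The visit schedule gives five visits (weeks 0, 12, 24, 36, 48) for most of these outcomes. There are four for β2-microglobulin ("urine β 2-microglobulin | X | X | X | | X") and two, weeks 24 and 48, for HBV DNA ("HBV DNA viral load | | | X | | X").

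**The concern.** Friedman's test needs every condition to be observed in the same block. Here the patient is the block and the visits are the conditions. A patient belongs to one arm only, so arm cannot be a condition. An analyst who follows the text has two options, and neither compares the treatments:

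- **Pooled over arms.** The p-value answers whether the outcome changes over time in the whole trial population. It can be significant when the arms behave identically and non-significant when they move apart.
- **Run separately by arm.** The two p-values describe each arm's own change. Concluding that the treatments differ because one is significant and the other is not is not a test of treatment.

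A shared time trend is what the plan itself expects for eGFR. The sample size section takes +2.89 for TAF and says that the "eGFR change value level is +5.92 after TDF dose adjustment". For any outcome on this branch, the report could therefore carry a p-value for time under a heading that promises a treatment comparison. A larger sample would not cure this.

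**Working it through.** **1. The statistic.** With N patients, k visits and R_j the sum over patients of the within-patient rank of visit j,

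χ² = 12 / [N k (k+1)] × Σ R_j² − 3 N (k+1), on k − 1 degrees of freedom.

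Arm does not appear. Each R_j is the TAF rank sum plus the TDF rank sum, so equal trends reinforce each other and opposite trends cancel. Two numerical checks agree. Shuffling patients between arms left the statistic at 1.042 (p = 0.903). Multiplying every value in one arm by 10 left it at 4.2529.

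**2. HBV DNA, two visits.** Let p patients be higher at week 48 and m higher at week 24, with N = p + m after ties are dropped. Then R_24 = p + 2m and R_48 = m + 2p, and the formula reduces to χ² = (p − m)² / N. This is a within-patient sign test of week 24 against week 48, again without the arm.

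**3. Inputs for the simulations.**
- From the sample size section: mean eGFR changes +5.92 and +2.89 (difference 3.03, half of it 1.515); SDs 4.26 and 7.69; two-sided 5% level; 40 per arm with 15% dropout, so 40 × 0.85 = 34 per arm. The plan's own 33 per arm is reproduced by a two-sample t calculation with difference 3.03 and SD 4.26 (32.02, rounded up), so these inputs are used as the plan uses them.
- Assumed, because the documents give no figures: baseline SD 10 for eGFR; log SD 1.0 and log-change SD 0.5 to 0.8 for skewed outcomes; the 30% fall and the ratios 0.8 and 1.25; equal correlation between visits; change as a linear ramp to week 48 or a step from week 12.

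**4. Results.** Share of 10,000 simulated trials per scenario with p < 0.05. Ranges cover the ramp and step profiles and, in the lognormal rows, both log-change SDs.

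| Scenario | Pooled Friedman | Mann-Whitney, week-48 change |
|---|---|---|
| Lognormal, both arms fall 30%, five visits | 84-100% | 4-5% |
| Same, four visits | 81-100% | 4-5% |
| Lognormal, ratios 0.8 and 1.25, either schedule | 4-5% | 51-89% |
| eGFR-like, +1.515 and −1.515, SD 4.26 | 4-5% | about 80% |
| Same, SD 7.69 | 4-5% | 34-35% |

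Further pooled Friedman results for eGFR-like data on five visits:
- Both arms at +2.89: 99.7-100% (SD 4.26) or 68-80% (SD 7.69), although the arms are identical.
- The plan's own +5.92 versus +2.89: 97-100%. With SD 4.26, identical arms give practically the same rate, so the result reflects time and not treatment.
- No change in either arm: about 5%.

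**5. By-arm use.** With no change at all, two independent 5% tests disagree in 2 × 0.05 × 0.95 = 9.5% of trials. With identical arms that change, exactly one arm is significant in 6-50% of trials (lognormal), in 9.5-20% (eGFR-like at +2.89, SD 4.26) or in 46-49% (SD 7.69).

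**The case against.** The strongest reply is that the defect is conditional. The plan says ANOVA or Friedman's test. ANOVA can carry the treatment comparison, and eGFR, the only outcome the trial is sized on, is less likely to go to the rank branch. If every outcome went to ANOVA, nothing would be lost. This stands as a limit on scope. It does not rescue the branch, because the plan gives no rule that keeps any outcome out of it, and protein creatinine ratio, β2-microglobulin, AST and ALT are plausibly skewed.

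Second, the magnitudes depend on chosen scenarios. The two diverging cases are built so that the trends cancel, which is a worst case. For eGFR it also departs from the plan's expectation that both arms improve. The effect sizes and SDs for skewed outcomes are not in the documents, and the high rejection rates with identical arms need a shared time trend. All of this is correct and bounds the figures. The absence of arm from the statistic needs no assumption.

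Third, the plan never says that Friedman's test would be run by arm. That is true. The by-arm rates only show that this reading does not save the method.

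Fourth, Mann-Whitney on raw change is not the only repair. Log-transforming skewed outcomes and keeping ANOVA would also be valid and would use all visits. Under the same lognormal model with diverging arms, Mann-Whitney on raw change had 49-53% power against 56-62% on log change (log-change SD 0.8), and 88-89% against 93-95% (SD 0.5). This is a fair point about the choice of remedy, not a defence of Friedman's test.

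**Conclusion.** The concern holds and must be fixed before analysis. Section 8.8.2 names a test that cannot make the comparison it is assigned, and nothing elsewhere in the plan supplies a between-arm rank test for these eight outcomes. This is a wrong method as written, not a missing detail.

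Its reach is limited to outcomes sent to the Friedman branch, and the plan does not let the reader count them. Within that branch the error can go either way: near-certain significance without any treatment difference when both arms share a clear trend, and no power beyond the 5% level when trends cancel. Confidence in the defect is high. The percentages depend on the assumptions listed above. No rate was simulated for HBV DNA, where the point rests on the algebra alone.

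**What to change.** In section 8.8.2:

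1. Delete Friedman's test as the between-arm method, and state in advance which outcomes are analysed non-parametrically.
2. For those outcomes, compare the arms with Mann-Whitney on the change from week 0 to week 48, and report a Hodges-Lehmann difference with its 95% CI. For positive, skewed outcomes the change may be taken on the log scale, if this is stated in advance.
3. Give HBV DNA its own line. It has no scheduled week-0 measurement, and entry requires "HBV DNA viral load levels ≤ 10 U/mL in the last 3 months" before joining. Either compare the week-48 values, or the proportions above the 10 U/mL entry limit, directly between arms, or name the screening value as the baseline.
4. For outcomes that stay with repeated measures ANOVA, write down the arm factor and the arm-by-time interaction, which the text leaves implicit.

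The downside of item 2 is that a single week-48 contrast ignores the intermediate visits. If they should count, pre-specify Mann-Whitney on each patient's mean change over the scheduled post-baseline visits. The team must make that choice before seeing the data.

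The cost is a short paragraph. No new data or visits are needed, and Mann-Whitney is already in the plan for NGAL.
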